19. MULTI-SITE RESEARCH*

N/A; this is not a multi-site study.

20. COMMUNITY-BASED PARTICIPATORY RESEARCH*

N/A

21. SHARING OF RESEARCH RESULTS WITH SUBJECTS*

There are no specific plans to share results with study subjects; study procedures do not include any type of diagnostic testing.

All results shared in published research will be in aggregate or summary format and will not include identifiable information about participants. Published results are available to the greater community at large, including study subjects.

22. SETTING

We will recruit patients from the surgery clinics of UMass Memorial Medical Center - strewn between University and Memorial campuses.

23. RESOURCES AVAILABLE

All research personnel listed on this study will read the protocol and receive the appropriate supervision and possess the appropriate experience (both higher education and related work experience) needed to fulfill their roles and complete their responsibilities for this study. All investigators and project staff are required to receive and complete IRB and HIPAA training.

The Principal Investigators will oversee all personnel and all research activities conducted within this study.

The Principal Investigator will have responsibility for the overall conduct of the project at this study site. They will have primary oversight of all study personnel. They will participate in the

INVESTIGATOR STUDY PLAN - REQUIRED

design and the execution of the respective study analyses and will be responsible for the reporting of study results. The Principal Investigators have extensive experience and expertise in surgical outcomes research and perioperative medicine.

The Programmer will perform a range of programming and data management activities essential to conduct of the project. S/he will develop study data bases, and perform analyses under the direction of the PI. Programmers at the Meyers Primary Care Institute all hold graduate level degrees and have vast experience working with administrative claims data for research purposes.

The Project Manager will assist the Principal Investigator and the Co-Investigators in implementing all aspects of the project. Under the direction of Principal Investigator, the Project Manager will be responsible for day-to-day coordination and oversight of the project, including: developing timelines, work allocation, workflow plans, monitoring project progress and task completion, monitoring spending and effort allocation, and managing correspondence and administrative tasks. S/he will monitor/manage ethics and regulatory approvals (IRB, HIPAA/DUA). The Project Manager will attend and plan for all project-related meetings as needed. S/he will work under the direction of the Principal Investigator to assist with all study activities, preparing IRB submissions and reports, and developing study materials such as development of data collection instruments and intervention-related tools. S/he will be responsible for maintaining communications with all parties participating in the project. She will maintain project documentation and will assist in developing and filing required project reports. Project Managers at the Meyers Primary Care Institute all hold graduate level degrees and have vast experience working on healthcare services research projects.

A research staff member will work under the direction of Principal Investigator, Project Manager and Research Manager to assist with all study activities. S/he will assist the PI and other project staff in managing the administrative activities of the project. S/he will prepare materials for team meetings, and will facilitate communication between all project staff through written correspondence, telephone, fax, and email. A research staff member will be trained to formulate walking prescriptions (with oversight from the PI) as well as conduct the 6MWD measurement. A nurse or senior clinician will be available during the time when a research staff member is conducting the 6MWD measurement.

The REDCap Administrator will be the contact with UMass for all REDCap administrative needs throughout the study. As the appointed REDCap administrator for the Meyers Primary Care Institute site, s/he will have access to all study data collected within REDCap.

All study personnel are required to undergo Human Subjects Training and hold a current CITI Human Subjects Training Certificate and will familiarize themselves with the study protocol and IRB documents.

Individuals have not yet been identified to fill the roles of programmer and research staff member. Once the staff has been identified they will be added into the eIRB system. No study staff will begin any study activities until they have been added into the eIRB.

INVESTIGATOR STUDY PLAN - REQUIRED

24. LOCAL RECRUITMENT METHODS

We will attempt to recruit 200 subjects from the surgery clinics affiliated with UMass Memorial Medical Center. We believe 200 subjects is the requisite number we need to successfully answer our research question. We believe the annual pool of eligible patients is more than 400. This accounts for a reasonable amount of refusal, surgery cancellation, and also loss to follow-up.

Typically, consultation with colorectal surgeon occurs after colonoscopy has detected a significant lesion. Once the surgeon and participant have agreed to a surgical plan, the surgeon will invite the participant to speak to our project staff member about the study.

For those participants agreeing, the research staff member (already on site based on having reviewed the appointment lists the day before) will obtain informed consent and conduct initial interview.

The research staff member will then ask the patient about falls, visual impairment, and chest pain to elicit any exclusion to eligibility.

We do not intend to provide stipends.

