Additionally, it would be important to analyze step counts from the pedometer and the percentage of days in which individual patients achieved prescribed targets. This would permit assessing whether any improvements in physical status resulted from the walking intervention. Conversely, if there is no improvement in physical status assessments, we could diagnose if nonadherence with the walking prescription was the reason. Finally, it would be helpful in guiding future research to calculate the time and cost required to recruit eligible patients as well as to assess patient satisfaction with the walking prescription.

INVESTIGATOR STUDY PLAN - REQUIRED

We therefore propose a study of 400 older adults scheduled for surgery with the following aims which will prepare us to conduct a larger trial focused on clinical outcomes.

Aim 1: To assess the impact of a walking prescription intervention on outcomes of endurance, balance, gait speed, strength, and self-reported function in patients with frailty.

Aim 1a: To estimate improvement in outcomes as a function of duration of the walking intervention.

Aim 1b: To re-estimate the effect of the intervention adjusting for the percentage of days each patient met his/her walking goal.

Aim 1c: To measure patient satisfaction with the walking intervention.

Aim 2: To measure the average time and cost required to recruit and follow up each patient.

Aim 3: Postoperative outcomes: we may also measure several postoperative outcomes

Change in six-minute walk distance from baseline

The number of steps per day in the hospital

Time to 100 steps at the day of discharge.

Discharge to skilled nursing facility

Length of stay

Thirty-day outcomes including serious complication, readmission, and death

Aim 4: Measure the performance of Edmonton frailty score for predicting 30 day outcomes including serious complication, readmission, death.

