9. STUDY TIMELINES*

The overall study timeline is two years from start of recruitment. The first year will focus on preparation (training on frailty measurement, scripting interviews, and testing the questions we ask) and recruitment of study subjects. Individual subjects will be actively involved for 30 minutes during their first appointment (not including time spent in clinic appointment), approximately 15 minutes during the day of their surgery, and potentially approximately ten additional minutes on their day of discharge from the hospital, though patient data collection will continue for up to one year after the day of surgery.

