Aim 1a: Self-reported function: We will administer the 12 items of the Veteran Rand (VR-12) in order to measure self-reported function.¹⁶ We will then calculate the summary physical component score (PCS) using a published algorithm.¹⁶ The algorithm norms PCS to range between 0 and 100, with 50 as a mean, and 10 as the standard deviation for the US population.

Aim 1b: Adherence with exercise: We will measure the percentage of days in which the participant meets his/her step count target for intervention patients and activity journals for both groups of patients

Aim 1b: Patient satisfaction: We will design a custom instrument to assess patient satisfaction with our intervention.

Aim 2: Time and cost to recruit 400 frail older adults: We will calculate the time and cost to recruit 400 patients. We will assess time in multiple ways: number of calendar days and number of working clinic days. For cost, we will assign an hourly wage for research staff member and RN efforts and then multiply by the number of hours required to perform recruitment, follow-up telephone calls, and follow-up assessments.

Aim 3: Postoperative outcomes: we may also measure several postoperative outcomes, including:

Change in six-minute walk distance from baseline

The number of steps per day in the hospital

Time to 100 steps at the day of discharge.

Discharge to skilled nursing facility

INVESTIGATOR STUDY PLAN - REQUIRED

Length of stay

Postoperative Recovery (measured via quality of recovery scale, abdominal surgery impact scale)

Thirty-day outcomes including serious complication, readmission, and death

Aim 4: Thirty-day outcomes including serious complication, readmission, and death

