Aim 1c: We will calculate the distribution of patient satisfaction with the intervention, using descriptive statistics, e.g., mean, percentiles, as well as a histogram. Using generalized linear modeling, we will measure patient satisfaction adjusted for changes in physical status. Given the possibility of co-linearity of physical status assessments, we will construct five separate models, one for each of the five physical status assessments.

Aim 2: We will calculate the average time and cost required to recruit each patient by taking the total time and cost divided by the number of patients we eventually enroll (i.e. 200 patients).

INVESTIGATOR STUDY PLAN - REQUIRED

Aim 3: In patients for whom we have recorded postoperative six minute walk distance and step counts, we will calculate change in six minute walk distance from baseline to day of discharge. We will also calculate steps per day and time to first 100 steps. We will calculate the average steps per day using postoperative days 1 and 2 given variation in the start time of surgery for the surgical day and time of transportation availability on the discharge date. For the rare patient leaving the hospital on postoperative day 2, we will only use postoperative day 1. For patients with serious complications requiring ICU stay, we anticipate no steps will be taken and will adjust for this in our analysis. We will measure time to walking at least 100 steps in a single bout, defined as continuous minutes walking at least 1 step/minute following example in the literature. Being able to walk 100 steps in a single bout approximates criteria used to predict successful discharge home from acute hospitalization. We recognize that some patients will not walk 100 steps and so we will adjust for this in our analysis (i.e. we will censor their data in survival analysis).

In terms of the other outcomes, we will compute length of stay in hours from the time of surgery until time of discharge. We will also perform chart review between 30 and 120 days after surgery to tabulate number of patients discharged to nursing home, readmitted at 30 days, dead at 30 days, or having a serious complication of 30 days.

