25. LOCAL NUMBER OF SUBJECTS

We will attempt to recruit 400 subjects who contribute to the ultimate analysis of this work.

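### The planned size is 400 subjects in Sections 4, 10 and 25 but 200 in Section 24 and in Section 13's Aim 2, and nothing reconciles the two

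*Combined protocol and SAP*

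**What the plan says.** Five sections of the combined protocol and SAP give a size.

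- Section 4 (Objectives): "We therefore propose a study of 400 older adults scheduled for surgery".
- Section 10 (Study Endpoints, Aim 2): "Time and cost to recruit 400 frail older adults".
- Section 25 (Local Number of Subjects): "We will attempt to recruit 400 subjects who contribute to the ultimate analysis of this work".
- Section 24 (Local Recruitment Methods) sets a recruitment target of 200 and adds: "We believe 200 subjects is the requisite number we need to successfully answer our research question".
- Section 13 (Data Analysis and Management, Aim 2) defines the average as "total time and cost divided by the number of patients we eventually enroll (i.e. 200 patients").

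Section 7, where a study-wide number would stand, is marked not applicable because there is one site. It therefore gives no total that could settle the matter.

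Section 24 supports its figure with a statement about supply: "We believe the annual pool of eligible patients is more than 400". It continues: "This accounts for a reasonable amount of refusal, surgery cancellation, and also loss to follow-up". No rate is given for any of these losses. On time, Section 9 says: "The overall study timeline is two years from start of recruitment". It places both preparation and recruitment in the first year.

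**The concern.** Sections 24 and 25 follow one another, describe the same single site, and give targets that differ by a factor of two. Aim 2 has the same split within itself: Section 10 plans the cost of recruiting 400, and Section 13 illustrates the divisor for that cost with 200.

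The number of participants is a basic design figure. Staffing, the recruitment period, ethics approval and the precision of every estimate depend on it. Here a reader cannot tell which figure governs, or which patients each one counts. Section 24 presents 200 as what is needed to answer the research question, while three other sections plan twice that. Its case that enough patients exist is made only for the smaller number. Aim 2 is meant to inform the planning of a larger trial, so it matters which patients its average covers.

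**Working it through.** **1. Can either figure be reproduced?** No. The document gives no significance level, power, effect size, standard deviation, precision target or dropout rate for a sample-size calculation. The check is therefore a comparison of texts.

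**2. The figures side by side.**

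| Section | Figure | What it is attached to |
|---|---|---|
| 4 | 400 | older adults scheduled for surgery |
| 10, Aim 2 | 400 | frail older adults recruited |
| 25 | 400 | subjects contributing to the final analysis |
| 24 | 200 | subjects to recruit, said to be the number required |
| 13, Aim 2 | 200 | patients eventually enrolled |

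The ratio is 400/200 = 2.

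**3. Could attrition explain it?** Going from 400 to 200 needs a loss of 1 − 200/400 = 50%. No such rate is stated. The labels also run the wrong way: the larger number is attached to patients in the analysis (Section 25) and the smaller to patients enrolled (Section 13).

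**4. Could screening explain it (400 screened, 200 randomised)?** Several features fit:
- Section 6 has separate criteria for screening and for the randomised trial.
- Section 11 seeks authorisation at screening to collect the Aim 3 outcomes.
- Aim 4 assesses the Edmonton score as a predictor of 30-day outcomes, for which patients who are screened but not randomised are useful.

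One feature does not fit. Section 10 describes its 400 as frail. Under Section 11, frailty is established by the screening score, so 400 frail patients cannot be the whole screened group unless everyone screened is frail. No passage states the 400/200 split.

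**5. Share of the pool.** Inputs are the targets of 200 and 400 and the annual pool at its stated floor of 400 (Section 24). The formula is share = target / (400 × years of recruitment).

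| Recruitment period | Target 200 | Target 400 |
|---|---|---|
| One full year | 200/400 = 50% | 400/400 = 100% |
| Two full years (assumption, same annual pool) | 200/800 = 25% | 400/800 = 50% |

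The pool is said to exceed 400, so these shares are upper bounds, but only for full 12- or 24-month periods. Preparation shares the first year with recruitment, and a shorter period would raise the shares.

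**6. Aim 2.** If a literal 200 were applied to the total cost of recruiting 400, the per-patient average would be inflated by 400/200 = 2. Section 13's working rule, however, is to divide by the number eventually enrolled; the 200 is a parenthetical gloss on it.

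**The case against.** The strongest reply is that the document describes two populations, 400 screened and 200 randomised, and merely fails to label them. The features in step 4 make this plausible. A reader might infer that Section 25's reference to subjects who contribute to the analysis rules it out, but it does not: screened patients who are never randomised supply Aim 3 and Aim 4 outcomes and so do contribute. The evidence against this reading is Section 10's word frail and the absence of any statement of the split. If it is what the sponsor intends, the protocol still has to say so.

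A second reply is that Section 25 is the section dedicated to the number of subjects, and it says 400, as do Sections 4 and 10. That is fair: a figure is stated where one would look for it. But Section 24 contradicts it immediately beforehand, in terms of what the research question requires.

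A third reply concerns the consequences. A reader might infer that 400 is unachievable. The document does not show this. Section 24 says its statement already allows for refusal, cancellation and loss; if the pool is net of these, 400 a year is not shown to be out of reach. Nor does Section 9 say that recruitment ends with the first year. A reader might also infer that Aim 2 will report a doubled cost. That does not follow, because the working rule uses actual enrolment. These replies limit the consequences but leave the contradiction in place.

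**Conclusion.** The inconsistency is real and stands in current text: 400 in three sections, 200 in two, a factor of two, with no reconciling statement. It needs correcting, and that conclusion rests on the direct conflict alone, above all between Sections 24 and 25.

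What can be said about recruitment is narrower. The pool argument is made only for 200. At 400 the target equals the stated floor of the pool for one full year, and the document does not make clear whether that pool is counted before or after losses. For Aim 2, the planned denominator is inconsistent, but no numerical error is shown.

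A reader might want to infer that the trial is underpowered at one size and adequate at the other. The plan does not support this. It specifies no between-arm test or error rates from which power could be computed, and the Aim 1 analysis is written as within-participant change against a minimal clinically important difference. The documents do not show which figure was intended.

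**What to change.** 1. State one number to be screened and, separately, one number to be randomised. Use them consistently in Sections 4, 10, 13, 24 and 25.
2. In Section 24, make the sentence on the required number match the chosen randomised number, or delete it.
3. Restate the pool sentence for that number and for the actual recruitment period, and say whether the annual pool is counted before or after refusal, cancellation and loss to follow-up.
4. In Section 13, Aim 2, delete the parenthetical 200 and divide by the number actually enrolled, over the same patients whose time and cost are in the numerator.

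The cost is protocol wording; correcting the inconsistency does not in itself call for extra patients. The downside is that the stated size or the recruitment margin may look less favourable once a single figure is fixed.

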6. INCLUSION AND EXCLUSION CRITERIA*

Inclusion criteria for screening - We will enroll participants age 50 and older undergoing any abdominal or thoracic surgery.

Inclusion criteria for randomized controlled trial - We will enroll participants age 50 and older undergoing any abdominal or thoracic surgery.

Exclusions for screening – non-adults, prisoners, Non-English language speaker for whom short form consent is not available.

Exclusions for randomized controlled trial - The exclusions we will apply pertain mainly to the measurement of 6MWD – (1) unstable angina or stable angina with minimal exertion or at rest (2) visual impairment such that walking impairs safety (3) fall within previous three months, (4) resting heart rate of more than 120, a systolic blood pressure of more than 180 mm Hg, or a diastolic blood pressure of more than 100 mm Hg (5) patient who does not walk independently (e.g. wheel chair; cane walking is ok)

Individuals who are not yet adults (infants, children, teenagers)

This study excludes anyone who is less than 50 years old; no children will be included in this study.

Pregnant women

Pregnant women will not be included.

Prisoners

Prisoners will not be included in the study.

Non-English language speaking subjects

INVESTIGATOR STUDY PLAN - REQUIRED

Non-English language speaking subjects for which an IRB approved short form is available will be included; patients speaking a language for which the UMass IRB does not have a short form consents available will not be included.

Adults unable to consent (adults lacking capacity)

Adults who are deemed cognitively impaired or unable to consent will be included; given the topic of study and the inclusion/exclusion criteria, it is possible that potential participants with impaired decisional competency will be identified for this study. If substantial cognitive impairment is indicated through the use of the MiniCog test, we will implement consent procedures consistent with those recommended for patients with cognitive impairment. This includes reviewing consent with a legally authorized representative and close monitoring of patients. If patients appear unduly distressed, they will be withdrawn from the study. Please see section # 30. Consent Process for additional details.

*See also section #18.

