16. RISKS TO SUBJECTS*

Potential Risks

INVESTIGATOR STUDY PLAN - REQUIRED

The proposed study poses minimal risks to the participants. There is a slight risk that research records (interview forms, interview notes, audio-recordings, transcripts, and electronic data) might be obtained by persons not authorized to do so. There is a slight risk that research data files might be compromised, and obtained or viewed by unauthorized persons. There is also a risk that the patient may feel uncomfortable answering some of the questions in the interviews. We will inform all patients during the informed consent process that they do not have to answer any questions that they do not want to. There is also a risk that the patient may fall. We screen patients initially based on prior falls to minimize this risk. In addition, there is screening for cognitive impairment for patients who may not fully appreciate risks of walking. The same screening process protects patients against development of chest pain or shortness of breath. We exclude patients with existing angina in such that small amount of walking or being at rest (i.e. class III or IV angina). We also have a physician or nurse on the premises at all times responsible for the patient if he or she were to develop shortness of breath, chest pain, or fall.

See also #14 Provisions to Monitor the Data to Ensure the Safety of Subjects, and #27 Provisions to Protect the Privacy Interests of Subjects.

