30. CONSENT PROCESS

During the patient's scheduled surgery clinic appointment, a surgery clinic staff member will then introduce the study and ask if the patient is willing to discuss the study with a study staff member after his/her surgery clinic appointment. If a patient expresses interest, the surgery clinic staff member will notify study staff member.

For patients who agree to speak, the study staff member will find a private room and discuss enrollment and informed consent. Prior to documenting written consent, the study staff member will determine if a patient needs to undergo cognitive testing. Criteria for this determination include presence in the electronic medical record of prior consent document such as for undergoing medical procedures signed by a person other than the patient, patient report of having somebody else sign for him or herself, mention of legal guardian in electronic medical record, or study staff members belief that the patient may be cognitively impaired. If legal guardian documentation in the electronic medical record indicates that medical decision-making requires guardian to sign consent, we will omit cognitive testing and proceed to obtain consent from the guardian and assent from the patient. Otherwise, to execute cognitive testing, the study staff member will administer the MiniCog test. We are waiving written documentation of consent, as the MiniCog presents no more than minimal risk of harm to subjects and involves no procedures for which written consent is

INVESTIGATOR STUDY PLAN - REQUIRED

normally required outside of the research context. If the patient passes the MiniCog assessment, the patient will sign a consent form to participate in the study. If the patient does not pass, we will obtain informed consent from a caregiver or surrogate and will ask the patient to indicate their assent. At the time of consent, the recruiter will also ask the participant and/or caregiver to sign a HIPAA authorization form for the purposes of chart review.

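### The patient is the only documented source for the fall, vision and chest-pain exclusions, even when someone else must consent on the patient's behalf

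*Combined protocol and SAP*

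**What the plan says.** Section 6 lists the exclusions for the randomised trial. Three depend wholly or partly on history: "unstable angina or stable angina with minimal exertion or at rest", "visual impairment such that walking impairs safety" and "fall within previous three months". The remaining ones (heart rate, blood pressure, independent walking) can be measured or observed.

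Section 24 describes how the three are found: "The research staff member will then ask the patient about falls, visual impairment, and chest pain to elicit any exclusion to eligibility".

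Section 6 also states: "Adults who are deemed cognitively impaired or unable to consent will be included". Section 18 repeats this. Section 30 gives two routes. If the chart shows that a guardian must sign, "we will omit cognitive testing and proceed to obtain consent from the guardian and assent from the patient". If the patient is tested and does not pass the MiniCog, "we will obtain informed consent from a caregiver or surrogate", again with the patient's assent.

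On the risk of falling, Section 16 says: "We screen patients initially based on prior falls to minimize this risk". It credits the same screening with protecting against chest pain and breathlessness, and names cognitive screening as a further protection for patients who may not appreciate the risks of walking.

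**The concern.** When a patient fails the MiniCog or has a guardian, the protocol does not rely on that patient's own consent. It does rely on the same patient's recall of falls over three months and account of chest pain. The person who consents is given no stated part in supplying that history.

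If staff follow Section 24 literally, a patient who meets a Section 6 exclusion could pass the screen and do the six-minute walk. If randomised to the intervention, that patient would then walk at home with step counts rising each week. The safeguard that Section 16 relies on would be weakest in a group that Section 18 treats as vulnerable. The matter is one of participant safety and correct application of eligibility; no endpoint or analysis depends on it.

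**Working it through.** The plan states no figure on this point, so there is none to reproduce. The check is of the text, followed by a rough sizing on assumed rates.

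**Is there a second source for the history?**

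- *Section 24 (recruitment):* the patient is asked. No other informant or record is named.
- *Section 11 (pre-visit chart review):* the listed variables cover demographics, functional status, body size, surgery and appointment details, plus a search for guardianship or cognitive impairment. Falls, vision and angina are not listed. The stated purposes of the list are to compare participants with decliners and to cue clinic staff.
- *Sections 6, 18 and 30 (consent):* a representative reviews or gives consent. No role in giving history is stated. Section 30 lets a guardian who is not present sign electronically through a link, so an informal conversation in clinic cannot be assumed.
- *Section 30 (HIPAA):* an authorisation for chart review is signed at consent, but no section directs that review to these exclusions.

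**Does the cognitive screen act as Section 16 implies?** Under Section 30 it is done only when certain signs are present, and it is skipped when a guardian must sign. A fail changes who consents; it does not exclude. It therefore does not keep out patients who may not appreciate the risks of walking.

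**Do other safeguards verify the history before the walk?**

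| Safeguard | Section | Verifies the history before the walk? |
|---|---|---|
| Nurse or more senior clinician at the six-minute walk, with listed stopping reasons | 10, 11 | No; acts on symptoms during the test |
| Physician or nurse on the premises | 16 | No; responds to events |
| Balance and chair-stand tests at baseline | 10, 11 | No; show current performance, not recent falls or angina |
| Prescription set in consultation with a study physician | 11 | No; follows the baseline walk |
| Weekly calls to intervention patients | 11 | No; later, and dependent on participant report |
| Close monitoring of impaired patients | 6, 18 | Not specified |

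**Rough size.** The three rates below are assumptions; the documents give none.

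- Share of recruits consented by a representative: 5% to 15%.
- Share of those with an excluding fall or symptom: 10% to 20%.
- Share of those exclusions that the patient does not report: 20% to 50%.

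Number affected = recruits × the three shares.

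- With 200 recruits (Section 24; Section 13, Aim 2): 200 × 0.05 × 0.10 × 0.20 = 0.2, up to 200 × 0.15 × 0.20 × 0.50 = 3.0.
- With 400 recruits (Sections 4, 10 and 25): 400 × 0.05 × 0.10 × 0.20 = 0.4, up to 400 × 0.15 × 0.20 × 0.50 = 6.0.
- Randomisation is 1:1 (Section 11), so about half would be assigned to walking: 0.1 to 1.5 of 200, or 0.2 to 3 of 400.

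These counts treat every recruit as entering the randomised trial.

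**The case against.** The strongest reply is that Section 24 offers one sentence in a recruitment summary. It does not forbid asking a caregiver or opening the chart. Section 11 says that interview scripts and data collection forms will be written and approved before data collection starts, and these may name further sources. The chart-review list is not presented as an eligibility checklist, so the absence of falls and angina from it proves little. Several safeguards reduce the consequences of a missed exclusion. The numbers are small and rest on assumption.

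Much of this stands. A reader might infer that the protocol rules out any source but the patient. It does not: it is silent, and the supportable claim is that the patient is the only documented source. A reader might also infer that patients are enrolled because they failed the MiniCog or have a guardian. Section 30 does not say so: they are eligible despite this, and it changes only who consents. Nor is home walking without any oversight, given the weekly calls and the physician's part in the prescription. That self-report is less dependable in these patients is a reasonable judgement, but the documents do not measure it.

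The gap itself remains. Staff who follow the protocol need not consult anyone else, and no listed safeguard checks the exclusion history before the first walk.

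**Conclusion.** The concern holds as a gap between the protection that Section 16 claims and the procedure that Sections 6, 18, 24 and 30 describe. It covers only the fall, vision and chest-pain exclusions, and matters most for patients whose consent comes from a guardian, caregiver or surrogate.

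The number affected is probably small: about 0.2 to 3 of 200 recruits or 0.4 to 6 of 400, roughly half of them assigned to walking. Those figures rest wholly on the assumed rates and on which of the two recruitment totals applies. A reader should not take them as a forecast of harm, because the documents give no rate of falls, impairment or under-reporting. The textual finding does not depend on them. The change is worth making because it strengthens a protection that the protocol itself relies on, at little cost.

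**What to change.** In Section 24, state that when consent comes from a guardian, caregiver or surrogate, in person or remotely, the same questions on falls, vision and chest pain are also put to that person. State that the chart is checked for these items under the HIPAA authorisation signed at consent. Both steps should be complete before the baseline six-minute walk.

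Apply the Section 6 criteria exactly as written to the combined information. A bare chart entry of angina should not exclude by itself, because Section 6 is narrower than that. Reconcile Section 16's account of the fall and cognitive screens with Sections 6, 18, 24 and 30.

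The cost is a few minutes per affected patient, possibly a minor IRB amendment, and a few more exclusions. No new staff are needed. One limit remains: a remote guardian may not know the recent history, so the chart check is needed as well.
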